12.0 Objectives and Rationale

12.1 * Overview

Briefly state the ***purpose of this study***. Give enough background and rationale to provide both scientists and lay members of the IRB and ACCTS with the basis for exposing human participants to the risks involved.

Zoster vaccine (Zostavax, Merck) is recommended for the prevention of herpes zoster (HZ) reactivation (shingles; painful blistering rash along the cranial, thoracic or lumbosacral dermatomes). It is recommended for individuals > 50 years without an underlying immune deficiency (HIV, malignancies, immunosuppression and transplantation). In non-immunocompromised individuals, zoster vaccine decreases HZ reactivation by 51-61%. In the U.S., 99.5% of adults >40 years have been infected with Varicella zoster virus (VZV) and are at risk of herpes zoster virus reactivation and its complications (acute or chronic PHN, osteonecrosis, herpes zoster ophthalmicus with visual impairment, increased risk of blindness and a four-fold risk of cerebral vasculitis-associated stroke). Chronic infections with persistent mycobacterial, helminthes and viruses are associated with increased susceptibility to other pathogens and decreased vaccination efficacy. Although chronic Hepatitis C virus (HCV) infection is not considered a clinically immunosuppressed state, it has been associated with persistent immune activation and decreased immune response to vaccination. Zostavax is routinely administered to chronic HCV patients. However, at present, no other study has documented the immune responses elicited by Zostavax in this population. This study aims to identify the innate and adaptive immune signatures elicited by zoster vaccination in individuals chronically infected with HCV as compared to healthy volunteers. Methods to be Results from this study could identify targets of potential vaccine optimization for this population and increase available knowledge on host immune response to chronic viral infections.

12.2 * Engaging Stakeholders: Describe any plans to engage other stakeholders (Scientists, practitioners, patients, advocacy groups, etc.) for hypothesis generation, or feasibility purposes.

The PI along with other members of the [name] laboratory were instrumental in the design of this study. Biostatisticians at the Rockefeller University provided additional statistical evaluations for the Clinical and Translational Science Center.

The team will identify multiple members of the patient community, as well as outreach and harm-reduction workers with experience referring HCV infected volunteers to clinical research, in order to engage patients in the design of the study, including aspects of recruitment, conduct, retention, and the analysis and sharing of results. Patients and other will be invited to face-to-face meetings with the research team and support staff (or teleconference if preferred), and will be compensated for their time /effort. Patient stakeholders engaged in this way are not expected to enroll into the study; any exploration of their enrollment would be made separately, free of undue influence

12.3 * Hypothesis

Describe the ***research hypothesis*** in a single sentence.

We hypothesize that individuals with chronic HCV infection will demonstrate impaired innate and adaptive immune responses following zoster vaccination.

12.4 * Aim(s)

Indicate how you will **address the hypothesis** (e.g., to compare groups, to estimate a parameter, to ascertain feasibility). Since the sample size determination is usually based on the primary aim only, the primary aim should be sufficient to justify the study.

AIM 1: Characterize the adaptive immune response to zoster vaccination in chronic HCV infection

Zoster vaccine will be administered to healthy and HCV-infected individuals. Volunteers serum, PBMCs, and plasma will be collected at screening, days 0, 3, 7, 14, and 42 and batched for analysis to limit variations. In order to fully evaluate the immune signature generated by the zoster vaccine, we will determine the frequency and functionality of specific PBMC populations using flow cytometry and ELISpot assays. We aim to compare the data generated from this study to other published human system immunology and/or vaccination studies. To achieve this aim, our research group has adapted a flow cytometry panel designed to limit variations in standardizing human immunophenotyping. This flow cytometry panel is also currently being applied to the HBV vaccine study (CRI-0844). We will analyze intracellular cytokine staining and expression of cell surface markers on immune cells. IFN-gamma ELISpot assay has been used in older HZ vaccine studies to evaluate T-cell immune response post-vaccination. Commercially available VZV-derived peptides pools will be used to stimulate PBMCs in the ELISpot assay. VZV-specific antibody production post-immunization would also be assessed using commercially available VZV-ELISA kits.

AIM 2. Characterize the innate immune response to zoster vaccination by RNA-Seq analysis

RNA-seq will be used to evaluate innate immune activation by evaluating the changes to the expression levels of interferon-stimulated genes pre- and post-vaccination. In this pilot project, RNA will be isolated with using commercially available PAXgene tubes to immediately stabilize intracellular RNA profile and traditional homogenization of isolated volunteer PBMCs in Trizol prior to cryopreservation. RNA-seq sample preparation and sequencing will be performed at the Rockefeller University Genomics Resource center. The [name] research laboratory, with their extensive experience with RNA-seq will perform analysis of this data. Genome-wide mRNA expression profiles will be compared between the 2 arms of the study, healthy and chronically HCV infected volunteers. Gene expression levels will be quantified in relation to a reference standard of External RNA Control Consortium (ERCC) controls – a calibrated panel of defined RNA molecules at defined concentrations that will be “spiked in” to each library preparation to serve as a universal reference across samples.

12.5 * Primary Outcome(s)

Indicate which **variable(s)** will be assessed to judge the primary specific aim. Give measurement units, if applicable.

We will measure the following parameter:

- **Serum zoster antibody levels by gpELISA expressed in (units/ml)**

12.6 * Secondary Outcome(s)

Indicate which **additional variable(s)** will be assessed to judge the secondary outcome(s). Give measurement units, if applicable.

- **Interferon-stimulated gene (ISG) expression in PBMCs expressed as fold-change (FCH) above baseline**
- **Serum biomarkers of innate immune activation (expressed in %)**
- **Responder cell frequency: VZV specific CD4+ T cells post-vaccination (expressed in %)**
- **Interferon-gamma response by ELISpot expressed as number of spot-forming cells per 10^6 PBMCs**

12.7 * Methods and Procedures

Please provide a description of the laboratory and clinical analyses and procedures that will be performed. Include the role of external collaborators and consultants when appropriate. Please refer to Help text for Guidance.

This study is an open-label protocol divided into the healthy versus chronic HCV volunteer arms. The study will be advertised in local newspapers and different online resources. Potential participants identified with the aid of the Bellevue Hospital Center Hepatitis clinic and other local physicians, will be asked to call [name] ([name]), if they are interested in the study.

Our aim is to screen and enroll 20 age-matched (\pm 5 years) and gender-matched individuals between 50 and 60 years of age into each arm of the study. Individuals recruited into the study must be HIV and hepatitis B negative, without a history of vaccination within the past month, no history of immunosuppressive therapy, active malignancies or herpes zoster reactivation. Baseline screening tests (HIV ELISA, hepatitis B anti-surface and core antibodies, hepatitis C antibody, viral load and genotyping, complete blood counts and a comprehensive metabolic panel) will be obtained prior to enrolling in the study. HCV viral load and genotyping: will be determined by clinical laboratory analysis. Patient blood samples will be sent to a CLIA certified reference laboratory for analysis.

The initial protocol was written in the summer of 2015, prior to the availability of the influenza vaccine for the current 2015 – 2016 season. It would be unethical to have interested participants delay receipt of their influenza vaccination prior to enrolling in this study. Also, a 3-month delay after participants' influenza vaccination would delay the progress of the clinical study, as we have already secured some funding for the study.

In addition, receipt of vaccination 4 weeks prior to entry into a zoster vaccination study has a precedent, namely the landmark study by Oxman et al. The FDA's approval of a license for use of Zostavax in 2006 cited this study¹.

Reference:

1. Oxman, M. N. *et al.* A vaccine to prevent herpes zoster and postherpetic neuralgia in older adults. *N Engl J Med.* 2005 Jun 2;352(22):2271-84.

In this study there will be a total of seven study visits (Screen I and II, Days 0, 3, 7, 14, 42). All enrolled volunteers will be given a single 0.65 mL dose of the live attenuated zoster vaccine (Zostavax, Merck & Co, Inc) on day 0 with follow-up visits on days 3, 7, 14, and 42. The most frequent adverse reactions, reported in subjects vaccinated with Zoster vaccine, were headache and injection-site reactions. Additional adverse effects have not been reported in individuals chronically infected with Hepatitis C virus. All women of child-bearing potential are required to use a highly effective form of contraception such as condoms, birth control pills, birth control injections, or intrauterine devices for three months following the vaccination. Any adverse reactions observed in women of child-bearing potential should be reported to: To report SUSPECTED ADVERSE REACTIONS or exposure during pregnancy or within three months prior to conception, contact Merck Sharp & Dohme Corp., a subsidiary of Merck & Co., Inc., at [name] or VAERS at [name] or www.vaers.hhs.gov.

At the Day 0 and Week 6 visit we will collect approximately 121 mL of blood during and at the other visits (Days 3, 7, and 14) we will collect 49 or 53 ml of blood respectively for research and clinical laboratory monitoring. Non-fasting blood samples will be drawn during the initial screening visit. Subsequent laboratory blood samples will be fasting for screening visit II and days 0, 3, 7, 14 and 42. Research blood will be separated into PBMCs, plasma and serum by the study PI. All samples will be stored in cryopreserved aliquots until batched assays prior to described assays.

HCV persistence has been associated with HCV-specific-CD8+T-cell exhaustion and bystander CD8+T-cell dysfunction. HCV-specific CD8+T-cell exhaustion is characterized by diminished *ex vivo* polyfunctionality, upregulation of negative co-stimulatory cell modulators, decreased cellular proliferation, interferon production and cytotoxicity. Effective immune responses to vaccination include the activation and expansion of antigen-specific memory B-cells and T-cells following antigen stimulation. Chronic HCV has been associated with impaired immune response to vaccination against Hepatitis A virus, influenza and most prominently Hepatitis B virus with 40-60% in chronic HCV versus 90-95% in healthy volunteers. Studies on HBV-vaccination of chronic HCV patients have identified impaired specific and non-specific CD4+T-cell immune in non-responders to HCV infection.

Flow cytometry, ELISpot and ELISA analyses will be performed on PBMCs to determine B-cell and T-cell proliferation and polyfunctionality. we will determine the frequency and function of specific PBMC populations using flow cytometry and ELISpot assays. For flow cytometry, we will utilize an antibody panel designed to limit variations in standardizing human immunophenotyping to assess intracellular cytokine staining and expression of cell surface markers on immune cells. IFN-gamma ELISpot assay has been used in older HZ vaccine studies to evaluate T-cell immune response post-vaccination. We will utilize commercially available VZV-derived peptide pools will be used to stimulate PBMCs in the ELISpot assay. VZV-specific antibody production post-immunization would also be assess using commercially available VZV-ELISA kits. A multiplex Luminex assay targeting TNF-alpha, IFN-gamma, IL-2, IL-4, IL-17 and other cytokines will be performed on plasma samples. Flow cytometry and multiplex cytokine assays will be performed with the assistance of the Translational Technology Core Laboratory Resource center.

Chronic HCV infection is associated with persistent innate immune activation and dampened cellular immune responses. Interferons (IFNs) are key mediators of the antiviral innate immune response, initiating expression of interferon-stimulated genes (ISGs) with numerous host protective effector functions. In chronic HCV, high pre-therapy expression of ISGs and persistent activation of the innate immune system negatively predict the response to IFN-based therapies and failure of viral clearance. Innate immune response will be determined by RNA-seq pre- and post-vaccination. RNA will be isolated using commercially available PAXgene tubes to immediately stabilize intracellular RNA profile, in addition to the traditional homogenization of isolated volunteer PBMCs in Trizol prior to cryopreservation. Blood will be collected into PAXgene tubes and isolated PBMCs will also be collected into TRIZOL for RNA isolation and RNA-seq analysis. RNA isolated from PBMC will be prepared by the Genomic Resource center and sequenced for genome-wide mRNA expression profiling. Genome-wide mRNA expression profiles will be compared between the two arms of the study (healthy and chronically HCV infected volunteers). Gene expression levels will be quantified in relation to a reference standard of External RNA Control Consortium (ERCC) controls – a calibrated panel of defined RNA molecules at defined concentrations that will be “spiked in” to each library preparation to serve as a universal reference across samples.

PBMC samples may also be analyzed by single cell resolution InDrop RNA-Seq (REFERENCE PMID: 26000487), established for immune response profiling in the [name] laboratory. Within a microfluidic device, individual cells and individual hydrogel “barcode beads” are co-encapsulated in water-in-oil droplets, in which reverse transcription tags nascent cDNA with cell-specific barcode sequences. After droplet breakage, library preparation and high throughput sequencing, reads can be assigned to individual cells by barcode for gene expression profiling. Using this approach, sufficient sampling can be achieved with relatively low input cell numbers and rare cells (i.e. dendritic cells, antigen-specific lymphocytes) are represented in resulting datasets.

In order to define the immune functions engaged by Zoster vaccination at single cell resolution, longitudinal PBMC samples will be analyzed by InDrop RNA-Seq. Data analysis will focus on first classifying cells by type (e.g. T cells, B cells, NK cells, classical monocytes, dendritic cells, etc.) using multidimensional clustering methods as implemented in the Seurat tool (REFERENCE PMID: 25867923). Next, differential gene expression patterns active in different cell subsets will be assessed over time, and the heterogeneity of these patterns will be evaluated at single cell resolution. We expect these results to complement bulk RNA-Seq results by providing greater detail on specific cell subsets and their respective transcriptional networks and response dynamics.

With the May 2019 IRB continuing review submission, [name] has been replaced by [name] as the Principal Investigator of this study. [name] has been listed as External Personnel and will not conduct any further data analysis or be involved with any protocol-related activities.

With the May 13, 2019 amendment, [name], a Guest Investigator in the [name] laboratory, will conduct the data analysis and review of the stored research samples collected in this study.

12.8 * Data Analysis

Describe method(s) of data analysis. Include the role of external collaborators as appropriate.

The primary analysis for the set of primary outcomes will search for statistical evidence of impairment in the innate and adaptive immune response in chronic-HCV subjects compared to age-matched Healthy Controls by testing the hypotheses that the variation from baseline to day 42 will differ between these two groups. To achieve this goal, we will apply two-sided paired t-tests and/or Wilcoxon tests for each one of the outcomes. Additionally, as a secondary analysis, we will fit a mixed-effects model that will use group (HCV – HC) and time (0,3,7,14, and 42 days) as fixed effects and a random intercept for each subject. This modeling strategy allows to infer about differences across time points, and also within time points, while controlling for multiple testing. Further evaluation of the immune signature generated by the zoster vaccine will be done with flow cytometry and ELISpot assays and qualitative comparisons with other

human system immunology and /or vaccination studies will be carried out. For the secondary outcomes, the analysis for the ISG expressions as measured by RNA-seq counts will be processed in *limma* package in R and the same formulation for mixed-effects model described previously will be applied to verify differences at gene-wise level. Serum biomarkers of immune activation will be compared across groups with paired t-tests and Wilcoxon test for each time point.

12.9 * Explain the rationale for the choice of statistical measures and the number of participants proposed for the study, including the power calculations when applicable.

A sample of n=40 (20 HCV / 20 HC) individuals provides 80% power at 1.6% (after Bonferroni correction for 3 outcomes) significance to detect minimum differences in biomarkers variation from baseline to day 42 as 1.08 standard deviations when applying two-sided paired t-tests. Since there is no preliminary data showing the degree of variability in the primary outcomes for the chronic HCV population, this pilot study will be valuable for future power analysis. To test for gene-wise differences between healthy and HCV-infected groups for a single time point, a sample size of n=20 individuals in each groups provides 80% power at 5% significance to detect effect sizes greater than 1.5 FCH (Fold-Changes), assuming a coefficient of variation as 40% and a depth of coverage greater than 20. Calculation was performed using the library RNASeqPower in R software version 3.2.1.

12.10 * Will samples be coded?

Yes No

If Yes, Please describe coding scheme consistent with GCP. If samples will not be coded, please provide justification for this proposed departure from GCP practice.

All samples will be coded with unique identifiers based on study number assigned to each individual upon study enrollment. Study volunteers' HIPAA protected information will not be associated with any research data. All computers used to store and analyze research data will be password protected. All data will be backed-up into the system maintained by Information Technology Service at the Rockefeller University.

If available, upload the Data and Sample Sharing Management Plan approved by RU IT.

Version	Title	Category	Expiration Date	Document Outcome	Checked Out	View Document
No Document(s) have been attached to this form.

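### Section 12.7 limits earlier vaccination only within the past month and neither excludes nor records earlier zoster vaccination, so repeat-dose responses may enter the HCV v healthy comparison

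*Combined protocol and SAP*

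**What the plan says.** The vaccination criterion is in 12.7 (Methods and Procedures). Besides negative HIV and hepatitis B status, volunteers must be "without a history of vaccination within the past month, no history of immunosuppressive therapy, active malignancies or herpes zoster reactivation". So a past zoster episode excludes at any time, but a past vaccination excludes only if it was recent.

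12.7 then explains the short window. The concern was influenza vaccine timing: participants should not have to postpone that vaccine, and a three-month wait would slow the study. It adds that "receipt of vaccination 4 weeks prior to entry into a zoster vaccination study has a precedent". Earlier zoster vaccination is not discussed.

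The background in 12.1 says of the vaccine that "It is recommended for individuals > 50 years without an underlying immune deficiency", and that "Zostavax is routinely administered to chronic HCV patients". Enrolment in 12.7 is of age-matched "and gender-matched individuals between 50 and 60 years of age into each arm of the study", 20 per arm. On day 0, "All enrolled volunteers will be given a single 0.65 mL dose of the live attenuated zoster vaccine".

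The primary outcome (12.5) is serum zoster antibody by gpELISA. The primary analysis (12.8) proceeds by "testing the hypotheses that the variation from baseline to day 42 will differ between these two groups". The secondary mixed model has group, time and a subject intercept, with no term for earlier zoster vaccination. The screening tests listed in 12.7 do not ascertain it.

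**The concern.** Read as written, the criteria admit someone given Zostavax two months or five years ago. For that person day 0 may already carry a vaccine effect, and the change to day 42 is a response to a second dose. The plan's own background makes such candidates plausible: the enrolment range lies almost wholly inside the recommended age group, and use in chronic HCV is described as routine.

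The study asks whether HCV impairs the response. Suppose repeat-dose rises are smaller. More previous recipients in the HCV arm would then imitate impairment, and more among the healthy volunteers would hide it. Equal shares would leave no false difference but would weaken the comparison. The ELISpot and VZV-specific CD4+ outcomes are exposed in the same way. Matching on age and gender does not protect against this, and if the exposure is not recorded nobody can later show that the bias is absent.

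**Working it through.** **Inputs from the documents.** 20 v 20, two-sided significance 1.6%, 80% power, detectable difference 1.08 SD of the change (12.9); outcome and comparison from 12.5 and 12.8.

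**Inputs assumed, because the documents do not give them.** Share previously vaccinated: p in the HCV arm, q in the healthy arm. Deficit of a repeat-dose rise: δ, in SD units.

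**Step 1: the plan's own figure.** For two independent groups the noncentrality is 1.08 × √(20/2) = 3.42 on 38 degrees of freedom. At two-sided 1.6% this gives power of 80.9%, with a detectable difference of 1.07 SD. The stated 80% is reproduced by an unpaired t-test. (A paired t-test on 20 pairs, which 12.9 names, would give 97.9%. That is a separate point.) The unpaired test is used below.

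**Step 2: add previous recipients.** With a true HCV deficit Δ and within-group SD of 1:

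- difference in mean change = Δ + (p − q)δ
- average variance = 1 + δ²[p(1 − p) + q(1 − q)]/2
- standardised difference d = difference / √variance, entered in the same noncentral t calculation

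**Step 3: no true HCV effect (Δ = 0), previous recipients in the HCV arm only (q = 0).**

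| p | δ | d | Rejection rate (nominal 1.6%) |
|---|---|---|---|
| 10% | 0.5 | 0.05/√1.011 = 0.050 | 1.7% |
| 10% | 1 | 0.10/√1.045 = 0.098 | about 2% |
| 20% | 0.5 | 0.10/√1.020 = 0.099 | about 2% |
| 20% | 1 | 0.20/√1.080 = 0.192 | about 3.5% |

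The bias is 0.05 to 0.20 SD. Simulation agrees with these rates to about 0.1 percentage point.

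**Step 4: true effect Δ = 1.08, same share in both arms, δ = 1.** The mean difference stays at 1.08 and only the variance grows.

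- 10% in each arm: d = 1.08/√1.09 = 1.034, power 77%
- 20% in each arm: d = 1.08/√1.16 = 1.003, power 74%

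**Step 5: true effect Δ = 1.08, previous recipients among healthy volunteers only.**

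- 10%, δ = 0.5: d = 1.03/√1.011 = 1.024, power 76%
- 20%, δ = 1: d = 0.88/√1.08 = 0.847, power 57%

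**Step 6: a different repeat-dose model.** Let a repeat dose give half of the first-dose rise, with a healthy first-dose rise of 1.08 to 2.0 SD. The true difference then shrinks as well. Equal shares give power of 74-76% at 10% and 66-70% at 20%. If a repeat dose gives no rise at all, the figures are 61-68% and 43-54%. The result depends strongly on an unknown repeat-dose response.

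**Step 7: would dropping previous recipients help?** With 20% in both arms, 4 of 20 are removed from each. At 16 v 16 the power for 1.08 SD is 69%, against 74% if they are kept (Step 4). Dropping them also breaks the age and gender matching.

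**The case against.** Five points can be made against the concern.

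- **Absence may be over-read.** Only section 12 is available, and the criteria appear in a methods narrative that reads like a summary. For example, 12.7 requires contraception but lists no pregnancy test or criterion. A fuller eligibility list may exist elsewhere in the application. This stands: the supportable statement is that the available text does not exclude or record earlier zoster vaccination.
- **Imbalance is not shown.** A reader might infer that the HCV arm came from the hepatitis clinic and the healthy arm from advertisements. 12.7 does not assign either route to an arm. The inference is plausible, but the documents do not support it as fact.
- **Direction and size are assumed.** 12.1 puts past VZV infection at 99.5% of US adults over 40, so even a first dose acts on existing immunity. The documents do not say that a repeat dose gives a smaller rise. This stands.
- **Large effects need strong assumptions.** A reader might infer a false-positive rate near 6%, or power near 44%. Those need 30% previous recipients in one arm, none in the other and a 1 SD deficit. The documents give no uptake figure, and routine use in practice does not measure uptake among volunteers seeking this vaccine.
- **This is a pilot (12.9), and enrolment may be over.** A 2019 note in 12.7 concerns analysis of stored samples. This changes the remedy but leaves the gap in place.

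**Conclusion.** The concern holds as a conditional one. The available text leaves earlier zoster vaccination unrestricted, unrecorded and unadjusted, and the plan's own background makes earlier recipients plausible. Whether any were or will be enrolled, in which arm, and with what repeat-dose response is unknown, so the documents do not support a claim that the comparison is biased or biased in a known direction.

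Under moderate assumptions the effect is modest. The false-positive rate is at most about 3.5% instead of 1.6%, with 10-20% v 0% in the HCV arm and a deficit of 0.5 to 1 SD. Power is 77-74% instead of 81%, with 10-20% in both arms and a 1 SD deficit. It is larger if previous recipients are concentrated among healthy volunteers or if repeat doses produce little rise. With 20 per arm, four people make up 20% of a group, so the point should be settled even in a pilot. It concerns comparability of the arms and makes no judgement on clinical use of repeat doses.

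**What to change.** **If enrolment is open:** add to the eligibility in 12.7 *no previous receipt of a zoster vaccine at any time*, for comparability of the arms. Check it with one history or record question at Screen I. Keep the one-month window for other vaccines.

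**If enrolment is closed:** ascertain earlier zoster vaccination from history and records before results are seen, and report it by arm. Keep all participants in the primary comparison. Add to 12.8 a pre-specified sensitivity analysis that excludes previous recipients or adjusts for earlier vaccination.

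**Also:** if an eligibility list elsewhere in the application already covers this, carry it into 12.7 or cite it there.

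**Cost:** a few candidates lost if enrolment continues, or a small record check if it has ended. The planned 20 v 20 and its power are unchanged.

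### The secondary mixed model, reused gene by gene for ISG expression, names no group-by-time term, so as written it does not test whether the vaccine response differs between arms

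*Combined protocol and SAP*

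**What the plan says.** Section 12.8 makes the comparison of change from baseline to day 42 the primary analysis. It then adds: "Additionally, as a secondary analysis, we will fit a mixed-effects model", whose terms are group (HCV or healthy) and "time (0,3,7,14, and 42 days) as fixed effects and a random intercept for each subject". The purpose follows: "This modeling strategy allows to infer about differences across time points, and also within time points, while controlling for multiple testing". For bulk RNA-seq, section 12.8 says "the same formulation for mixed-effects model described previously will be applied to verify differences at gene-wise level", with counts processed in limma.

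Four other places bear on what this model has to deliver:

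- Section 12.3 hypothesises "impaired innate and adaptive immune responses following zoster vaccination".
- Aim 2 in section 12.4 proposes "evaluating the changes to the expression levels of interferon-stimulated genes pre- and post-vaccination".
- Section 12.6 defines the outcome as "Interferon-stimulated gene (ISG) expression in PBMCs expressed as fold-change (FCH) above baseline".
- Section 12.9 sizes the RNA-seq part "To test for gene-wise differences between healthy and HCV-infected groups for a single time point".

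No group-by-time interaction and no contrast from this model is named anywhere.

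**The concern.** With main effects only, the HCV-healthy gap is forced to be the same at days 0, 3, 7, 14 and 42. The group coefficient is then a difference in average level, and a pre-vaccination visit contributes to it. It gives no visit-specific group difference, although the plan promises inference within time points. It also does not test a difference in response, which is what the hypothesis and Aim 2 call for.

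For ISGs this matters in both directions. Section 12.7 describes persistent innate activation in chronic HCV, so a day-0 gap is plausible.

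- If both arms respond alike, that standing gap can be read as a difference in vaccine response.
- If HCV patients start higher and respond less, the two effects have opposite signs and can cancel.
- If fold-change above baseline is the modelled variable, the baseline gap drops out, but a deficit confined to one or two visits is diluted in the average.

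Separately, a mixed model does not control multiple testing by itself, and no adjustment across visits or genes is named.

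**Working it through.** **The plan's own figures.** The documents give no power figure for the mixed model, but the two in section 12.9 reproduce.

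- Change to day 42: two independent groups of 20, difference 1.08 SD of change, two-sided 1.6%, noncentral t with 38 df. Power is 80.9% (stated: 80%). At 5% the same contrast has 91%.
- Gene-wise, one time point: n = 2(1.96 + 0.84)² × (1/20 + 0.40²) / (ln 1.5)² = 20.05 per group (stated: 20). This is a comparison of levels at one visit, not of change.

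**What each model estimates.** On simulated complete data, the fitted additive model's group coefficient was 1.042, equal to the gap averaged over the five visits (1.042). In a second data set, the group × day-42 coefficient from the interaction model was −0.633, equal to the directly computed difference in change from day 0 to day 42 (−0.633).

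**Illustration of size.** From the documents: 20 per arm, five visits, 1.08 SD of change. Assumed, because the documents give no variances or response profile: total SD 1 at each visit, within-subject correlation ρ = 0.7 (range 0.5 to 0.8 in brackets), baseline gaps of 0.2, 0.5 and 0.8 SD, and 5% two-sided tests.

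- Additive group term: a t-test on subject means, variance ρ + (1 − ρ)/5 = 0.7 + 0.06 = 0.76, 38 df.
- Day-42 change contrast: SD of change √(2(1 − ρ)) = 0.775, so 1.08 SD of change is D = 1.08 × 0.775 = 0.837. Power is 91% at any ρ.
- Fold-change reading: mean of the four changes, variance 1.25(1 − ρ). With k affected visits the standardised difference is 1.08 × (k/4) × √(2/1.25) = 0.342k, which does not depend on ρ.

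*1. Identical responses, baseline gap only*

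| Gap (SD) | Group term rejects | Change contrast rejects |
|---|---|---|
| 0.2 | 11% [10–13] | 5% |
| 0.5 | 42% [39–51] | 5% |
| 0.8 | 81% [77–89] | 5% |

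*2 and 3. No baseline gap, deficit D at k post-vaccination visits, day 42 always among them.* On levels the group term's expected value is kD/5.

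| k | Group term, levels | Group term, fold-change | Change contrast |
|---|---|---|---|
| 1 | 9% [8–14] | 18% | 91% |
| 2 | 22% [15–41] | 56% | 91% |
| 3 | 43% [28–73] | 88% | 91% |
| 4 | 66% [45–93] | 99% | 91% |

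*4. HCV higher at baseline, deficit D at all four later visits.* The expected group term is gap − 4D/5 = gap − 0.669.

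| Gap (SD) | Expected group term | Group term rejects | Change contrast rejects |
|---|---|---|---|
| 0.2 | −0.47 | 38% [21–75] | 91% |
| 0.5 | −0.17 | 9% [5–31] | 91% |
| 0.8 | +0.13 | 8% [6–14] | 91% |

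In the last row the estimate points away from impairment although the response is impaired at every visit. At ρ = 0.7 these results agreed with 50,000 simulated trials per scenario. A small run of fitted mixed models for the 0.5 SD row (150 runs, z-tests) gave 14% for the additive term and 94% for group × day 42, which is loose confirmation only.

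**The case against.** The strongest reply is that section 12.8 lists factors and gives no formula. Inference within time points needs the interaction, and section 12.9 sizes a comparison at a single visit, so visit-specific contrasts were probably meant. That is a fair reading of intent. It does not settle the matter: the text names only the two main effects, and a single-visit comparison of levels is still not a difference in change from baseline. Section 12.7 also records that a different investigator took over the data analysis in 2019, which makes the written specification matter more.

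Counts and fold-change can be reconciled as input scale and reporting scale, since a log-scale model with day 0 as a time level yields fold-change as a contrast. That stands, and it makes the fold-change column above the less likely reading. But the reconciliation itself works only if day-0 contrasts by group are in the model.

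The illustration uses a 5% test and an effect size borrowed from the biomarker calculation, whereas genome-wide testing would be stricter. At an assumed 0.1% per gene and ρ = 0.7, a 0.5 SD baseline gap is flagged 5% of the time rather than 42%, and the change contrast has 45% power rather than 91%. The sizes shift; the mismatch between the quantity tested and the question does not. Including day 42 in every scenario also favours the day-42 contrast: for a deficit at days 3 and 7 only, that contrast has 5% power and the averaged fold-change term 56%. This is a reason to name contrasts at every visit.

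Finally, the model is secondary and the study is a pilot. Both are true and limit the seriousness.

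**Conclusion.** The concern holds. Fitted as written, the secondary model does not estimate a difference in vaccine response and cannot support the within-visit inference claimed for it. The interaction is omitted rather than expressly excluded, and the primary day-42 comparison is untouched. The consequence falls mainly on ISG expression, because this is the only between-group model that section 12.8 names for bulk RNA-seq.

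The averaging result is exact for complete, balanced data; with missed visits the group term becomes a weighted average. The rejection rates depend on the assumed gaps, correlation and response patterns and show possible size, not a forecast. This should be fixed before the model is fitted, but it does not threaten the primary analysis.

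**What to change.** In section 12.8, write the model as group + categorical time + group × time with a subject random intercept. Define the tested quantity as the HCV-minus-healthy difference in change from day 0 at each post-vaccination visit, with day 42 the main contrast for the primary outcome. State whether ISG counts or fold-change above baseline is modelled. Use the same group × time contrasts in limma with subject as the blocking factor. Name the multiplicity adjustment across visits and the false discovery rate method across genes.

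The cost is one model line and named contrasts, with no new data: four extra parameters on 40 × 5 = 200 observations. Using the interaction model's residual variance (200 − 40 − 8 = 152 df), the day-42 contrast has 92% power for 1.08 SD of change at 5%, and 81% if Bonferroni splits the level over four visits (1.25% each). There is one real trade-off: if fold-change is modelled and the deficit is equal at all four visits, the averaged term (99%) beats a single-visit contrast (91–92%). If that pattern is expected, the average of the four change contrasts can be named as an additional contrast from the same model.
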